1 INTRODUCTION

1.1 STUDY BACKGROUND AND RATIONALE

Approximately 19-34 % of all people with diabetes will at some time in life develop a diabetic foot ulcer (DFU).¹ People with diabetes are especially prone to develop foot ulcers because of different diabetic complications, especially angiopathy and peripheral neuropathy.

The DFUs are often hard to heal and the treatment is long-lasting. The DFUs result in lower physical and mental quality of life and affects social relationships.² The treatment is also very costly,^{1, 3} it has been estimated that 25-50 % of diabetic inpatient care is related to DFUs.⁴ Despite extensive treatment, all DFUs do not heal but some end in amputation. People with diabetes are at a 25-fold risk of amputation and every 20 second a person somewhere in the world has the foot amputated because of diabetes.⁵ 85 % of these amputations are preceded by a foot ulcer⁶ and many of these ulcers and amputation could have been prevented.⁷

Total contact cast (TCC) as gold standard treatment of DFUs

Plantar DFUs often are the result of a combination of foot deformities that increase plantar pressures when the person walks and that the person keeps walking despite high pressure and ulcers because he or she has lost sensation in the feet because of sensory neuropathy. Literature reviews and international guidelines^{8,9} recommend non-removable knee-high offloading devices, for example, a total contact cast (TCC) to treat plantar DFUs, as this offloads the ulcer from mechanical loading all day and night. Still, TCC is not accepted by all patients and is contraindicated in a number of cases because of negative side-effects. Most of these side-effects are the consequences of immobilizing the ankle joint, which impairs gait and results in lower ambulatory activity. For example, side-effects include reduction of joint flexibility, weight gain, muscle atrophy, sick leave from work and social isolation.¹⁰ In addition, a TCC can give secondary ulcers why weekly visits to the hospital is necessary to change casts. For these reasons, TCC is only used for a minority of the patients for whom it could be beneficial, despite being the gold standard treatment.¹¹

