2.7 TIMING OF OUTCOME ASSESSMENTS

Table 1 below lists outcomes and time points for assessments (base-line, 4 weeks into treatment, and 1, 6 and 12 months after treatment end). For the 4 week into treatment and 1 month post-treatment assessments, a visit window of ± 1 week will be used. For the 6 and 12 months post-treatment assessments, a visit window of ± 1 month will be used.

Table 1. Overview of variables and assessment methods.

Variable (scale level: nominal=N, ordinal=O, interval=I)	Assessment method	Assessment occasion				
		Treatment period		Follow-up after treatment end		
		Base- line	4 weeks	1 month	6 months	12 months
Ulcer healing (N)	Clinical observation + blinded photo	X	X	X		
Skin complications (N)	Clinical observation + blinded photo	X	X	X		
Glycemic control (I)	Blood sample (HbA1c) ^a	X	X	X	X	X
BMI (I)	Measurement of weight and height	X	X	X	X	X
Gait function (I)	10 meter walk test ^{b 17}	X	X	X	X	X
Gait function (I)	Timed up and go ^{b 18}	X	X	X	X	X
Balance (O)	Berg balance scale ^{b 19}	X	X	X	X	X
Muscle atrophy (I)	Calf circumference ^{a 20}	X	X	X	X	X
General quality of life (O)	RAND-36 ^{c 21} , EQ-5D-5L ^{c 22}	X	X	X	X	X
Disease-specific quality of life (O)	DFS-SF ^{c 23}	X	X	X	X	X
Physical activity (I)	ActivPAL ^{d 24}	X	X	X	X	X
Physical activity (O)	National Board of Health and Welfare's indicator questions ²⁵	X	X	X	X	X
Bone mass density (I)	DXA ^e (heel bone)	X		X	X	X
Locus of control (O)	Questions from MHLC-C ^{c 26}	X		X	X	X
Ankle range of motion (I)	Goniometer ^{a 27}	X		X	X	X
Ankle strength (I)	Dynamometer ^{a 28}	X		X	X	X
Adherence to therapeutic shoes (O)	Questions from Q-TFA ^{c 29}	X		X	X	X
Treatment satisfaction (O)	Visual analogue scale ^c		X	X		
New ulcers, amputations, death, Charcot foot (N)	Patient file and self-report ^c				X	X
Health care consumption (O) ^f	Patient administration systems and self-report ^c			X	X	X
Sick leave from work (I) ^f	Self-report, ^c Swedish Social Insurance Agency's system			X	X	X

^aStandardized method, ^bfunction test, ^cquestionnaire, ^dactivity monitor, ^eDual-energy X-ray absorptiometry ^ffor the of health-economic analysis.

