5.3 SAFETY ASSESSMENTS

5.3.1 ADVERSE EVENTS

Adverse events that are judged to be related to the offloading devices (shoe or TCC) will be classified as adverse device effects (ADE) and serious adverse device effects (SADE).³² ADE include, but are not limited to, skin abrasions, blisters, sleep disturbances, issues with gait and balance, etc. SADE include, but are not limited to, new foot ulcers that result in amputation (major amputation = above ankle, minor amputation = below ankle), sepsis, etc.

Averse events that are not related to the offloading devices are classified as adverse events (AE) and serious adverse events (SAE).³² AE include, but are not limited to, skin abrasions or new foot ulcers on the contralateral foot and not related to the device, etc. SAE include, but are not limited to, death, amputation, onset of acute Charcot foot, sepsis, etc. (not related to the offloading device). However, in accordance with previous studies on similar patient populations, not all AE and SAE will be included as the patient population suffers from multiple co-morbidities and therefore a high incidence of illness and hospital admissions unrelated to the DFU and offloading devices can be expected.³³ Therefore, all ADE and SADE will be assessed, but only certain types of AE and SAE that are of particular interest, such as, amputation, death and onset of acute Charcot foot.

ADE, SADE, AE and SAE will be assessed with the aid of questionnaires, CRF, photographs of ulcer and skin, and patient files.

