6.1.3 SAFETY ANALYSES

Safety endpoints during the treatment period will be reported as summary statics (number and percentage) per study group. They will be categorized as AE, SAE, ADE and SADE (see point 5.3 above) and the proportions will be compared between the study groups with statistical tests for nominal scale data, that is, Chi-square test and presenting exact p-values and two-sided 95% CI.

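### The plan has no cumulative between-arm comparison of new foot ulcers during treatment, and the pooled ADE comparison can dilute or, in some settings, reverse a difference in them

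*SAP*

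**What the plan says.** **Reporting and comparison.** SAP 6.1.3 opens with "Safety endpoints during the treatment period will be reported as summary statics (number and percentage) per study group" and continues: "They will be categorized as AE, SAE, ADE and SADE (see point 5.3 above) and the proportions will be compared between the study groups". The test is a chi-square with two-sided 95% CIs. No comparison by type of event is specified, and the section does not say whether the percentages count participants or events.

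**Category content (SAP 5.3.1).** For device-related events, "ADE include, but are not limited to, skin abrasions, blisters, sleep disturbances, issues with gait and balance, etc". For serious ones, "SADE include, but are not limited to, new foot ulcers that result in amputation", with sepsis also listed. For events unrelated to the device, "AE include, but are not limited to, skin abrasions or new foot ulcers on the contralateral foot and not related to the device, etc". The same section then limits AE and SAE collection to selected types, giving amputation, death and acute Charcot foot as examples.

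**Other places where a new ulcer might appear (SAP 2.7, Table 1).**
- The row beginning "Skin complications (N" is marked at baseline, 4 weeks and 1 month after treatment. SAP 6.1.2 tests such nominal endpoints separately at each time point.
- The row beginning "New ulcers, amputations, death, Charcot foot (N" is marked only at 6 and 12 months after treatment.
- The recurrence analysis in SAP 6.1.2 starts after healing.

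**Importance given to ulcers.** SAP 1.1 says of the comparator: "In addition, a TCC can give secondary ulcers why weekly visits to the hospital is necessary to change casts".

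**The concern.** The documents treat secondary ulcers as a harm serious enough to shape the visit schedule, and one that can lead to amputation. Yet the only comparison that covers the whole treatment period mixes them with events of very different weight. SAP 1.1 also says that immobilising the ankle impairs gait under TCC, so the non-ulcer part of ADE may well be commoner in that arm.

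Two consequences follow. If the minor events are common in both arms, a real difference in ulcers, in whichever direction, is swamped. If they are much commoner with TCC, the pooled percentage can favour the shoe even when the shoe causes more ulcers. Fewer adverse events with the shoe is part of the overarching objective in SAP 1.2, so a pooled result in that direction is likely to be quoted.

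**Working it through.** **Step 1. Where is an ulcer that begins during treatment compared between arms?**

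| Event | Where it is compared |
|---|---|
| Device-related, leads to amputation | SADE |
| Device-related, no amputation | Not named; ADE by default, unless judged serious on another ground |
| Contralateral, not device-related | AE in the definition, but collection of AEs is then restricted |
| Any ulcer visible at the 4-week visit | Skin complications, if that term includes ulcers (not stated) |
| Appears and closes between scheduled assessments | Only the pooled category |

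The cast technicians record ulcers and complications 1-2 times a week (Protocol, paragraph on visits in both groups). The information is collected, but no analysis adds it up over treatment for ulcers alone.

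**Step 2. Inputs for the size.** The plan states no safety event rate and no power for safety, so there is no figure to reproduce. The group sizes are 56 per arm (minimum, SAP 2.3) and 150/2 = 75 per arm (target, SAP 2.3, with 1:1 allocation from SAP 2.1). The test is a two-sided 5% chi-square without continuity correction. All rates below are assumptions. A participant counts once, and ulcers (u) and other ADEs (o) are taken as independent:

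any ADE = 1 − (1 − u)(1 − o)

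Probabilities come from exact enumeration of both binomial distributions.

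**Step 3. Dilution.** With equal o in both arms, the pooled difference is (1 − o) × (u_shoe − u_TCC). For u = 15% v 5%, the 10-point difference shrinks to 8 points at o = 20% and to 5 points at o = 50%.

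| Other ADEs, both arms | Any ADE, shoe v TCC | Excess detected, 56/arm | 75/arm |
|---|---|---|---|
| 20% | 1 − 0.85×0.80 = 32% v 1 − 0.95×0.80 = 24% | 15.5% | 19.0% |
| 50% | 1 − 0.85×0.50 = 57.5% v 1 − 0.95×0.50 = 52.5% | 7.2% | 9.8% |
| Ulcers tested alone | 15% v 5% | 43.2% | 55.4% |

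By symmetry, the same figures apply if TCC has the 15% and the shoe the 5%.

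**Step 4. Reversal.** Keep ulcers at 15% v 5% and set the shoe's other ADEs at 30%, so any ADE with the shoe is 1 − 0.85×0.70 = 40.5%. The pooled percentages are equal when o_TCC = 1 − (0.85×0.70)/0.95 = 37.4%. Above that, the sign favours the shoe.

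| TCC other ADEs | Any ADE, shoe v TCC | Shoe significantly better, 56/arm | 75/arm |
|---|---|---|---|
| 40% | 40.5% v 43.0% | 4.3% | 5.5% |
| 50% | 40.5% v 52.5% | 23.7% | 33.1% |
| 60% | 40.5% v 62.0% | 62.0% | 76.8% |

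**Step 5. Limits of a separate comparison.** At ulcers 10% v 5%, testing ulcers alone detects the excess in 16.1% of trials (56 per arm) or 21.7% (75 per arm).

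**The case against.** A reader might infer that device-caused ulcers are compared only inside pooled ADE. The documents do not support that. Skin complications has its own test, with blinded photographs and one assessment during treatment after baseline, and it may include ulcers. Ulcers that lead to amputation go to SADE. Placing the remaining device-related ulcers in ADE is an inference from lists that are expressly open-ended.

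A reader might also infer that ulcer counts will go unreported, or that one pooled test decides Objective 2. Neither follows. The first sentence of SAP 6.1.3 does not rule out itemised reporting. Objective 2 asks about a difference in adverse events, and Protocol Table 1 assigns it many separately analysed measures.

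Nor do the documents suggest that the shoe causes more ulcers: the background names secondary ulcers as a TCC harm. The 62-77% reversal needs a 30-point TCC excess of minor effects. At a 10-point excess it is 4-6%, and below about 37% with TCC the sign does not reverse.

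These points narrow the claim. They do not supply the missing analysis: a single in-treatment test of an undefined variable is not a cumulative comparison of new ulcers.

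**Conclusion.** The gap is real but moderate. The plan specifies no cumulative between-arm comparison of new foot ulcers during treatment, and its pooled ADE comparison is a poor substitute.

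Dilution is the firmer part. It needs only that other ADEs are not rare, and in the cases shown it cuts the chance of detecting a 15% v 5% difference from 43-55% to 7-19%. Reversal is conditional: it needs minor ADEs to be clearly commoner with TCC, which the background makes plausible but does not quantify. Both results rest on assumed rates, on independence, on counting participants and on the default placement of ulcers in ADE. This should be amended in the SAP; it does not undermine the primary analysis.

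**What to change.** Add to SAP 6.1.3:

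> Participants with one or more new foot ulcers starting in the treatment period will be counted over all cast technician visits, for device-related ulcers and for all ulcers regardless of attribution, on the index and the contralateral foot. The number and percentage will be compared between groups as a separate safety outcome, with the risk difference and two-sided 95% CI.

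In SAP 2.7 or 5.2.2, state whether skin complications includes new ulcers. In 5.3.1, state which category takes a device-related ulcer without amputation.

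Keep the four pooled comparisons. Making them merely descriptive, or adding a separate abrasion and blister test, is not needed to close this gap.

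The cost is a few lines of SAP text and one or two table rows from technician records and photographs that the protocol already requires. The downside is one or two more comparisons without multiplicity adjustment, and low power for small excesses (16-22% at 10% v 5%). The gain is mainly an interpretable estimate with its interval, not a decisive test.

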6.1.4 BASELINE DESCRIPTIVE STATISTICS

Baseline characteristics will be summarized and presented for each study group, including demographic variables (sex, age, education level, living conditions, body mass index,), disease-related variables (diabetes type, diabetes during, glycemic control), foot-related variables (history of previous foot ulcers and amputations, foot deformities), index foot ulcer characteristics (site, ulcer area, depth, infection grade, duration), peripheral artery disease (toe pressure, TcPO₂), neuropathy (assessed with Ipswich Touch Test and Vibratip), and other variables (activity level, use of tobacco etc.).

Variables measured on a nominal scale will be presented as number (%), continues variables will be presented as mean (standard deviation).

6.1.5 SUB-GROUP ANALYSES

There is some debate whether non-removable offloading devices (such as TCC) are effective and safe to use for people with peripheral artery disease and infected DFU. For this reason, sub-group analyses will

be conducted for people with impaired circulation and more infected DFU at baseline, for the primary outcome (healing) and adverse events.

6.1.6 TABULATION OF INDIVIDUAL PARTICIPANT DATA

No individual participant data will be listed.

6.1.7 EXPLORATORY ANALYSES

Activity data will be collected with the ActivPAL activity monitor during 7 days after each of the 5 assessment visits to the physiotherapist. These data (on sitting, standing, walking, etc.) will mainly be analyzed in an exploratory manner, to investigate differences between study groups, trends over time, etc.

6.1.8 SENSITIVITY ANALYSES

The primary outcome will be analyzed on the ITT data set, per protocol dataset, and ITT dataset using multiple regression as a sensitivity analysis to test the robustness of the results. Multiple imputation will also be used as a sensitivity analysis for the primary outcome (see point 6.2).

6.2 MISSING DATA

Missing primary outcome data will be investigated through multiple imputation as a secondary sensitivity analysis of the primary outcome, as in previous study on devices for DFU healing.³³

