2.3 SAMPLE SIZE

The sample size calculation was performed using <http://powerandsamplesize.com/Calculators/Compare-2-Proportions/2-Sample-Non-Inferiority-or-Superiority>. Primary outcome is proportion of healed ulcers after 12 weeks of treatment. Based on the literature and our feasibility study the proportion of healed ulcers after 12 weeks treatment is estimated to 90% with sealed shoe or TCC.^{15, 16} If accepting $p=0.05$, a statistical power of 80% and a non-inferiority limit of 10%, 112 participants are

needed. To compensate for attrition of participants during the long-term follow up of secondary outcomes, the aim is to recruit 150 participants. The participants will be randomized to treatment with sealed therapeutic shoe or TCC. However, if it turns out that it is too difficult to recruit 150 participants, the recruitment of participant will end when the primary end point (healing at 12 weeks) has been observed for 56 participants per group, giving a total of 112 which fulfils the sample size calculation.

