3.3 ANALYSIS POPULATIONS

The primary outcome (ulcer healing) will be analyzed both on the ITT dataset, that is, on all randomized participants, and on the per protocol dataset, including only patients who were exposed to the intended intervention at least 80% of the treatment days, as judged per above (point 3.2). Secondary outcomes (including adverse events and adverse device effects) will only be analyzed on the ITT dataset.

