6 STATISTICAL ANALYSES

6.1 ANALYSIS METHODS

6.1.1 ANALYSIS OF THE PRIMARY EFFICACY ENDPOINT(S)

Primary efficacy endpoint is ulcer healing at 12 weeks, defined as complete epithelialization which is maintained for a minimum of 14 days (as required by the FDA).³¹ Healing is thus a single endpoint assessed on a nominal scale.

Ulcer healing will be assessed by the cast technician at the local hospital who redress the DFU, approximately 1-2 times per week (depending on the status of the DFU) in both groups. The cast technician will also photograph the DFU so it can be assessed by another person, blinded to group allocation.

In the analysis of the primary endpoint, the ITT dataset (analyzed with and without adjustment for covariates) and the per protocol dataset (analyzed without adjustment for covariates only) will be used. For the non-adjusted analyses, crude risk ratio (RR) or OR will be calculated to assess the impact of offloading device type on ulcer healing. For the adjusted analysis, baseline variables (sex, age, education level, living conditions, diabetes type and duration, glycemic control, BMI, history of previous foot ulcers and amputations, foot deformities, index foot ulcer characteristics, number of active ulcers, use of tobacco, peripheral artery disease, and neuropathy, see point 5.1) will be included as candidates in a logistic multiple regression, using backward selection and a p-value of 0.10 as cut-off for removal.

Participants for whom the 12 week observation is missing will be categorized as “not healed”. The statistician conducting the analysis will be blinded to group allocation.

The proportion of healed ulcers in each study group will be calculated, and the results will be presented as RR or OR and corresponding 95% CI.

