6.1.2 ANALYSIS OF THE SECONDARY ENDPOINT(S)

The secondary analyses are not dependent on the findings of the primary endpoint. No adjustment for Type 1 errors will be used as only one or a few statistical tests will be conducted for each secondary endpoint.

The secondary endpoints are time to healing and measures listed in Table 1. Each secondary endpoint is measured between one and five occasions during the study. The ITT dataset will be used for all analyses of secondary endpoints. Adjusted analyses will only be conducted for certain secondary endpoints that are of particular interest.

Time to healing will be compared between the study groups using survival analysis. Kaplan-Meier survival curves will be produced for the two study groups with median healing times and 95 % CI. Participants for whom the ulcer has not healed will be treated as censored and their date of trial exit or date of last available assessment will be used to calculate their duration in the trial. Hazard ratio with

95% CIs will be presented. Treatment effect will be explored using a Cox proportional hazards model including stratification factors (ulcer area and depth at baseline, periphery artery disease and infection grade) initially.

Survival analysis as above (but without adjustment) will also be used to compare ulcer recurrence after healing between the study groups. Recurrence rates at 12 months after healing will also be compared.

The analysis of the other secondary endpoints will be conducted according to scale level (nominal, ordinal or interval; Table 1) and compared at each time point (base-line, 4 weeks into treatment and 1, 6 and 12 months post-treatment) using the ITT dataset without adjustment for covariates: t-tests for ordinal and interval data if the assumptions of the t-test is fulfilled (normal distribution and equal variances), otherwise Wilcoxon rank sum test will be used. The Chi-squared test or generalized linear regression method will be used for nominal scale data. For each comparison both exact p-values and two-sided 95% CI will be reported.

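### The SAP gives no missing-data method for the visit-based secondary outcomes, so their ITT comparisons at 6 and 12 months rest on those measured and can be biased if dropout differs by arm

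*SAP*

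**What the plan says.** SAP 3.3 defines the main population as "the ITT dataset, that is, on all randomized participants", and SAP 6.1.2 carries it over: "The ITT dataset will be used for all analyses of secondary endpoints". Apart from the survival analyses and the health economic analysis, SAP 6.1.2 then compares the secondary endpoints separately at each time point, "using the ITT dataset without adjustment for covariates: t-tests for ordinal and interval data if the assumptions of the t-test is fulfilled", with a Wilcoxon test otherwise and chi-square or generalized linear regression for nominal data.

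The SAP has two rules for missing values, both for the primary outcome. In SAP 6.1.1, "Participants for whom the 12 week observation is missing will be categorized as" not healed. In SAP 6.2, "Missing primary outcome data will be investigated through multiple imputation as a secondary sensitivity analysis of the primary outcome"; SAP 6.1.8 repeats that scope.

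Some secondary endpoints do have a way of dealing with incomplete follow-up. For time to healing, "Participants for whom the ulcer has not healed will be treated as censored", at trial exit or last available assessment. For recurrence, "Survival analysis as above (but without adjustment) will also be used to compare ulcer recurrence after healing between the study groups". New ulcers, amputations, death, Charcot foot, health care consumption and sick leave draw on patient files or administrative systems as well as self-report (SAP Table 1).

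The plan expects losses. SAP 2.3: "To compensate for attrition of participants during the long-term follow up of secondary outcomes, the aim is to recruit 150 participants". SAP 2.6 provides for participants lost to follow-up, and SAP 4.4 names clinical reasons, death and refusal among the causes.

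**The concern.** A t-test, Wilcoxon or chi-square test at 12 months can only use people with a 12-month value. Once anyone is missing, the ITT label and the planned method cannot both hold for the visit-based outcomes. Extra recruitment protects precision but does nothing about selection.

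Selection that differs by arm is plausible on the documents' own account. The background sections say the cast impairs gait, lowers activity and is not accepted by all patients. Status during treatment may therefore differ between arms, and with it who returns later. If so, a long-term difference in gait, balance or quality of life could appear or be masked without any true effect. These outcomes serve Aims 2 to 4, and EQ-5D-5L also feeds the cost-utility analysis. The primary conclusion is not affected.

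**Working it through.** **1. The attrition allowance.** SAP 2.3 gives 112 needed and 150 recruited. Implied loss = 1 − 112/150 = 38/150 = 25.3%. In the other direction, 112/(1 − 0.25) = 149.3, rounded up to 150. So 25% is consistent with the plan but is not stated in it. Under the fallback, recruitment stops once 56 per group (112) have been observed at 12 weeks. No allowance then remains: a 25% later loss leaves 112 × 0.75 = 84.

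(The 112 itself, at 90% in both arms, margin 10%, one-sided 0.05 and 80% power, comes out at 111.3 *per arm*, not in total. That is a separate matter and nothing below depends on it.)

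**2. When an available-case difference is biased.** In one arm let *d* be the share missing and *g* the observed mean minus the missing mean, in SD. Full-arm mean = (1 − d) × observed + d × missing, so observed − full = d × g. The bias of the difference between arms A and B is therefore d_B·g_B − d_A·g_A. The documents give neither *d* by arm nor *g*, so these are assumptions:

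| d_A / d_B | g_A / g_B | Bias (SD) |
|---|---|---|
| 25% / 25% | 0.5 / 0.5 | 0.125 − 0.125 = 0 |
| 20% / 30% | 0.5 / 0.5 | 0.15 − 0.10 = 0.05 |
| 15% / 35% | 0.5 / 0.5 | 0.175 − 0.075 = 0.10 |
| 25% / 25% | 0 / 0.5 | 0.125 − 0 = 0.125 |

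Status-related dropout alone is not enough. The product d × g has to differ between arms.

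**3. Simulation.** Assumed inputs: 75 per arm (150/2), visit correlation 0.6, 25% dropout overall depending on the week-4 value with odds ratio 1.5–7.4 per SD, and no true difference at 12 months. The test is the planned unadjusted two-sided t-test at 0.05.

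| Scenario | Bias (SD) | Type I error |
|---|---|---|
| Rate and mechanism the same in both arms | about 0 | about 5% |
| Same dependence on status, arms 0.5–0.8 SD apart at week 4 (so dropout rates differ) | 0.01–0.12 | 5–10% |
| Dropout status-related in one arm only | 0.06–0.19 | 6–18% |

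Repeat runs move the bias figures by about 0.01 SD. An estimate that conditions on earlier visits had bias of about 0.005 SD or less in every scenario. Dropout there depended only on observed values, so the data were missing at random by construction.

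**4. Hand check of the type I errors.** With 25% lost, 75 × 0.75 ≈ 56 per arm remain, and the standard error of the difference is √(2/56) = 0.189 SD. A bias of *b* shifts the test statistic by b/0.189, and rejection is Φ(−1.96 + shift) + Φ(−1.96 − shift).
- b = 0.06: shift 0.32, rejection about 6%.
- b = 0.12: shift 0.63, rejection about 10%.
- b = 0.19: shift 1.01, rejection about 17%.

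These agree with the simulation.

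**5. What earlier data exist.** SAP Table 1 collects baseline, 1-month and 6-month values for these outcomes. Most also have a 4-week value; bone density, locus of control, ankle range, ankle strength and shoe adherence do not. A person lost at 12 months would usually have left usable data, which the per-visit test ignores.

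**The case against.** The strongest reply is that the problem may be small or absent. If dropout depends on status in the same way and at the same rate in both arms, the between-arm difference is unbiased however strong the dependence. That is correct, so a reader should not infer that these tests are valid only if losses are unrelated to condition, or that the long-term differences will be biased. The documents support worse gait in a cast during treatment. They do not support a gap of 0.5–0.8 SD, or that worse-off participants leave, or that they leave in one arm only. At the weak end of the range type I error is essentially nominal, and the upper figures need strong, asymmetric dropout.

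Two more stronger readings are tempting and fail. One is that no secondary endpoint has any handling of incomplete follow-up. Time to healing and recurrence are handled by censoring, and a missed visit need not mean missing data for file- or register-based outcomes. The activity-monitor data are mainly exploratory under SAP 6.1.7. The other is that the plan itself sets 25% attrition; that figure is only implied by 112 and 150.

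What stands is that the visit-based outcomes have no method at all, in a follow-up where the plan expects losses. Whether dropout matches across arms cannot be known in advance.

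**Conclusion.** The point holds for the visit-based secondary outcomes only. Their comparisons at 6 and 12 months are available-case comparisons labelled ITT, with no model, imputation or sensitivity analysis for missing values. They *can* be biased if dropout differs by arm in rate or mechanism. The size runs from about 0 to 0.19 SD, with type I error from about 5% to 18%. The upper end requires status-related dropout in one arm only, with an odds ratio of 7.4 per SD. The SDs, correlation, dropout by arm and mechanism behind these figures are all assumptions. At worst the bias is about one standard error of the comparison, enough to affect how a secondary result is read. The sponsor should change this, since the remedy uses data already collected.

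**What to change.** Amend SAP 6.1.2 and 6.2 together:

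- **Interval-scale visit-based outcomes.** Make the main analysis one likelihood-based repeated-measures model per outcome, using all collected visits: arm × visit, baseline included, unstructured covariance. Five visits need 5 × 6/2 = 15 covariance parameters, so name a simpler fallback structure in case of non-convergence. Report the arm difference at each visit from the model.
- **Ordinal and nominal visit-based outcomes.** Use multiple imputation that includes earlier visits, with an effect estimate that can be pooled across imputations. Use the same approach for the EQ-5D-5L values entering the cost-utility analysis.
- **Sensitivity analyses.** Keep the planned per-visit tests here, described as available-case. Add a missing-not-at-random analysis, for example shifting imputed values by a stated range in SD, separately by arm.
- **Deaths and never-healed participants.** State how each enters these analyses. The protocol times the later visits from healing and SAP 2.7 from treatment end, so the reference point for people who never heal must be reconciled.
- **Attrition.** State the assumed rate, and what the fallback stop at 112 means for the long-term comparisons.

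The cost is SAP wording, modest extra analysis work and reliance on a model. Missing at random is a weaker assumption than available-case tests need in general, so moving to it is a gain and not a cost.
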